6.3.3 Phlebotomy for Target Engagement, Cytokine Levels and Biomarker Analysis

Subjects will provide additional blood samples for biomarker analysis at Day 1, Day 28, and Day 84 visits. Target engagement will determine whether the subject's immune system has responded to BCG. In general, whole blood will be either collected and utilized for biochemical / metabolic assays, or spun in EDTA-containing tubes with plasma being frozen for cytokine analysis of IIR and / or AD biomarkers. Remaining plasma may be used for other biochemical analyses. Peripheral blood mononuclear cells (PBMCs) will be isolated from the cell pellets, some of which will be frozen for later culturing and cell-stimulation studies. Other PBMCs will be further isolated into subpopulations of cells and frozen for epigenetic analyses (e.g. ATACseq) and possibly subject to other immunostaining or quantitative biochemical assays.

60 ml (3.9 tablespoons) of blood will be collected for these analyses at the Day 1, Day 28, and Day 84 visits for a total of 180 ml (12.2 tablespoons) over the course of the study. Blood processing will occur on site at MGH. Blood samples will be de-identified, codified, and stored on-site at the [name] Lab biorepository. Blood samples will be stored for research until they are used, damaged, or otherwise unfit for analysis.

6.3.4 Lumbar Puncture for Immune and Biomarker Analysis

Lumbar punctures (LP) will occur at Baseline and Day 84 visits. Lumbar punctures will be performed after a minimum of an 8 hour fast. The subject will be positioned seated or lying on his/her side on the examination table. Standard protocols will be used employing palpation to identify the L3-4, L4-5 or L5-S1 vertebral interspaces, sterile conditions, local lidocaine anesthesia, and use of standard of care spinal needles. Clinical judgement will be used to determine the optimal spinal needle type/size for each participant. Lumbar punctures will be performed by qualified, experienced practitioners. Approximately 25 mL of CSF at each designated visit will be collected. A small portion of this volume will be used for analysis of cell count with differential, total protein, and glucose. The remainder will be spun and cells isolated from supernatant. Supernatant will be frozen for later immunoassays. Cells will be frozen for later biochemical analyses. Subjects will also complete a brief REDCap survey after the LP in which they will answer questions about the tolerability of the procedure. After the LP is complete, subjects will be given time to eat breakfast or have a snack before continuing with the visit.

If a subject has difficult back anatomy or is particularly overweight, and the physician or nurse practitioner does not feel comfortable performing the LP because they are not able to locate the proper lumbar landmarks, the subject will be scheduled to undergo the LP under fluoroscopy at MGH Interventional Radiology. Fluoroscopy time will vary person to person. The average radiation dose is 0.18 millisieverts (mSv), or the equivalent of 21 days of natural background radiation.

CSF samples will be de-identified, codified, and stored on-site at the [name] Lab biorepository. CSF samples will be stored for research until they are used, damaged, or otherwise unfit for analysis.

6.3.5 Vaccination Site Monitoring

Prior to the first vaccination, both deltoids will be inspected to confirm there is no evidence of previous BCG vaccination and no obvious symptoms that would contraindicate vaccine injection. At the Day 28 visit, prior to the second injection, the vaccination site will be inspected for any signs of local infection. At the Day 84 visit and if indicated by subject-reported AEs, the site of vaccination on the arm will be examined and any visible reactivity will be recorded.

6.4 Neurocognitive Assessments

6.4.1 Montreal Cognitive Assessment (MoCA)

The Montreal Cognitive Assessment (MoCA) is a commonly utilized questionnaire in clinical trials and research settings to measure levels of cognitive impairment.⁵⁴ The MoCA measures five areas of cognitive function: orientation, visuospatial, attention and calculation, recall, and language. The MoCA (version 8.1) will take approximately 15 minutes to complete. The MoCA will be administered at the Screening visit to determine subject eligibility (MoCA ≥ 18) and at the Outcome visit.

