3.2 Study Objectives

The primary objective of this study is:

1. To determine the most promising biomarkers of IIR and neurodegeneration in blood and CSF in terms of feasibility of measurement, technical specifications, and BCG response of assays.

The secondary objectives of the study will be:

1. To evaluate clinical neurobehavior changes from Baseline, including (MoCA, RBANS, NPI-Q and FAQ) following BCG vaccination.
2. To assess the safety and tolerability of BCG vaccination in healthy older adults and older adults with MCI.

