4.1.1 Inclusion Criteria

Study subjects meeting all of the following criteria will be allowed to enroll in the study:

1. Individuals between the ages of 55-80;
2. MoCA ≥ 18 ;
3. Normal cognition as defined by MoCA ≥ 26 or MCI as defined by the NIA-AA Workgroup (2011) and MoCA score between 18 and 25 (inclusive);
4. Education level, English language skills and literacy indicates subject will be able to complete all assessments;
5. Ability to provide informed consent;
6. Willing and able to complete all assessment and study procedures, including blood and lumbar punctures, and clinical assessments;
7. If on cholinesterase inhibitor and/or memantine, doses are stable for 3 months prior to baseline;
8. Negative test results for HIV antibody and Tuberculosis (QuantiFERON) at screening;
9. No prior BCG exposure either through birth vaccinations (born in North American) or BCG bladder cancer treatment.
10. Documentation of current flu season vaccination dated at least 14 days prior to baseline visit.

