6.2.2 Baseline Visit/BCG Vaccine 1 (Day 1)

All subjects who pass screening will return to MGH CNY for the Baseline visit. At this visit, all baseline clinical measures will be collected, and the first BCG vaccine injection will be administered. The Baseline visit will occur within 28 days of the Screening visit. If necessary, baseline measures may be collected up to 3 days before the Day 1 vaccination visit. The visit will take approximately three hours and will include:

- Vital signs
- Assess any changes to medical history, concomitant medications and/or adverse events
- Neurobehavioral assessments
 - RBANS
 - NPI-Q
- Phlebotomy for biomarker research
- Fasting lumbar puncture for biomarker research
- First BCG vaccine administration followed by 30 minutes of monitoring

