6.4.2 Repeatable Battery for the Assessment of Neuropsychological Status Update (RBANS)

The RBANS⁵⁵ is a commonly used 25-minute, standardized neurocognitive battery. The RBANS measures five neurocognitive domains, with twelve subtests measuring cognitive decline or improvement with immediate memory (List Learning and Story Memory), visuospatial/constructional (Figure Copy and Line Orientation), language (Picture naming and Semantic Fluency), attention (Digit Span and Coding), and delayed memory (List Recall, List Recognition, Story Memory, and Figure Recall). The RBANS has been shown to be effective at both detecting and characterizing forms of dementia. The Delayed Memory domain has been shown to be particularly sensitive to discriminating mild cognitive impairment (MCI) due to Alzheimer's disease from controls, and also is predictive of cerebral amyloid burden. The RBANS will be administered at the Baseline and Outcome visits.

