8 BIOSTATISTICAL ANALYSIS

8.1 Statistical methods

This is a single-site, open-label pilot clinical trial in which twelve older adult volunteers with normal cognition or MCI will be recruited for BCG vaccination with the intent of generating preliminary descriptive data on IIR and neurobiological biomarker effects and evaluate tolerability, safety and study feasibility. No sample size calculations are performed as no prespecified comparisons are planned. Statistical analyses will describe baseline characteristics of the sample and change in biomarkers, safety and clinical measures, with pre-post paired t-tests or non-parametric equivalents (Wilcoxon sign-rank) used to evaluate within subject change. All outcomes in this pilot study are considered exploratory and no claims are attached to them, thus multiple comparison correction is not applied. A P value <0.05 will be considered significant. Findings will be used to inform the design of subsequent placebo-controlled trials of BCG vaccination for prevention and/or disease modification of Alzheimer's disease and related disorders.

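### The Screening MoCA selects and splits the cohorts and is also the only pre-vaccination MoCA, so MoCA change is biased: downward in the normal cohort, in an unknown direction in the MCI cohort.

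*Combined protocol and SAP*

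**What the plan says.** Section 4.1.1 requires a MoCA of at least 18 and defines the two cohorts partly or wholly by that score. One is "Normal cognition as defined by MoCA ≥ 26", with no further clinical criterion named. The other is "MCI as defined by the NIA-AA Workgroup (2011) and MoCA score between 18 and 25 (inclusive".

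Section 6.4.1 says when the MoCA is given: "The MoCA will be administered at the Screening visit to determine subject eligibility (MoCA ≥ 18) and at the Outcome visit". The schedule in 6.1 and the visit lists in 6.2 agree. The Baseline list in 6.2.2 has RBANS and NPI-Q but no MoCA, and "The Baseline visit will occur within 28 days of the Screening visit". Version 8.1 is used at both MoCA visits.

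Secondary objective 1 in 3.2 is "To evaluate clinical neurobehavior changes from Baseline, including (MoCA, RBANS, NPI-Q and FAQ) following BCG vaccination". Section 5.2 confirms that everyone receives active treatment. Section 8.1 plans within-subject pre-post tests (paired t or Wilcoxon signed-rank) and adds "A P value <0.05 will be considered significant". It also calls all outcomes exploratory, with no claims attached.

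For comparison, on the other cognitive battery 6.4.2 says: "The RBANS will be administered at the Baseline and Outcome visits". RBANS plays no part in eligibility.

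**The concern.** A MoCA score is a true level plus measurement error. Admitting people because a particular score was high favours those whose error was positive on that day, so their next score is expected to be lower even if nothing has changed. If the admitting score is also the pre-value, that drop is counted as change after vaccination. The plan does not mention this, and with no control arm nothing in the design subtracts it.

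At stake is the reading of one of the four instruments that 3.3.2 lists for detecting beneficial or harmful effects. A fall in the normal cohort could be taken for a harmful signal, or could mask a small improvement.

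There is also a wording conflict. The objective speaks of change from Baseline, but neither the MoCA nor the FAQ is given at the Baseline visit.

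**Working it through.** **No figure to reproduce.** The plan gives no MoCA SD, reliability, expected change or source distribution, and no sample size calculation. All distributional inputs below are therefore assumptions, shown as ranges.

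**Inputs from the documents**
- Cuts on the Screening score: 26 or more (normal); 18 to 25 (MCI) (4.1.1).
- Test: paired pre-post, P<0.05 (8.1), taken as two-sided.
- Cohort size: about 10 each (3.1, twenty participants), or 6 each if the twelve in 8.1 are split equally. Sections 3.1 and 8.1 need to be reconciled; both sizes are used here.

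**Assumed inputs**
- Measurement error SD s: 1 to 2 points.
- Normal source: mean m 25.5 to 28, true-score SD t 1.5 to 2.
- MCI source: mean 19 to 24, true-score SD 2.5.
- No treatment effect, no practice effect, independent errors.

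**Formula.** Observed SD S = sqrt(t² + s²); reliability r = t²/S². For a cohort chosen on the Screening score,

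expected change = −(1 − r) × (mean Screening score of those selected − m).

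Scores are whole numbers, so the cuts are placed at 25.5 (normal) and at 17.5 and 25.5 (MCI). Below, φ and Φ are the standard normal density and distribution functions.

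**Normal cohort (one-sided cut).** Excess of the selected mean over m = S × φ(a)/(1 − Φ(a)), with a = (25.5 − m)/S.

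| m, t, s | S | r | a | excess | expected change |
|---|---|---|---|---|---|
| 28, 1.5, 1 | 1.803 | 0.692 | −1.387 | 0.300 | −0.308 × 0.300 = −0.09 |
| 27, 2, 1.5 | 2.500 | 0.640 | −0.600 | 1.148 | −0.360 × 1.148 = −0.41 |
| 25.5, 1.5, 2 | 2.500 | 0.360 | 0 | 1.995 | −0.640 × 1.995 = −1.28 |

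Simulation with rounding and the 30-point ceiling gives −0.10, −0.42 and −1.30 for these rows. The change was negative in every setting run.

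A paired t-test then gives P<0.05 with probability about 5% to 31% at n=10 and 5% to 18% at n=6, against a nominal 5%.

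A second set of assumptions (source mean 26 to 28, observed SD 1.5 to 2.5, reliability 0.7 to 0.9) gives −0.02 to −0.53: the same sign, but smaller.

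**MCI cohort (two-sided window).** Excess = S × (φ(a) − φ(b))/(Φ(b) − Φ(a)), with a = (17.5 − m)/S and b = (25.5 − m)/S. The sign turns where the window is symmetric about the mean: (17.5 + 25.5)/2 = 21.5. With t = 2.5 and s = 2, S = 3.202 and r = 0.610:
- m = 24: a = −2.030, b = 0.469; excess = 3.202 × (0.0508 − 0.3575)/0.6591 = −1.490; change = +0.390 × 1.490 = +0.58.
- m = 21.5: change = 0.
- m = 19: the mirror image, −0.58.

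**Both cohorts pooled.** With 10 per cohort, normal source mean 25.5 to 27 and SD 2, and MCI source mean 21.5 to 24, the mean change is −0.01 to −0.57 and the rejection rate about 4% to 15%. A lower MCI source mean makes the pooled drift more negative.

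**Separate Baseline MoCA.** When a fresh Baseline score is the reference and the Screening score only selects, the expected change with no treatment effect is 0.00 in both cohorts in every setting run.

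**The case against.** The strongest reply is that nothing rests on this. Section 3.3.2 does not expect marked cognitive change, and 8.1 attaches no claims to any outcome and uses the results only to plan later placebo-controlled trials. That stands as a reason to rate the point minor. It does not remove the bias: 8.1 offers the exploratory status as the reason for not correcting for multiplicity, and still calls P<0.05 significant.

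A second reply is that the large values need extreme inputs. That also stands. A fall beyond 1 point needs a source mean at or below the cut of 26 together with reliability of 0.50 or less. With more reliable scores and a source mean above the cut, the shift is a few tenths of a point.

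A third is that repeating version 8.1 may produce a practice gain that offsets the fall. It may, but that is a separate bias of unknown size, and an alternate form would leave the selection effect in place.

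A reader might go further and infer that the MCI cohort must rise, so that selection alone would look like a BCG benefit in MCI. The documents do not support this. MCI entry needs the NIA-AA criteria as well as a score in a window cut on both sides, and the source distribution is not given. If both cohorts came from one pool with mean 23 to 26, that pattern would appear (normal −0.19 to −1.39, MCI +0.07 to +0.91), but nothing in the plan establishes such a pool. Nor is a cohort comparison of MoCA planned: the between-group wording in 3.3.1 concerns biomarkers.

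**Conclusion.** The point holds in a limited form. The Screening MoCA sets entry, splits the cohorts and is the only pre-vaccination MoCA, in a trial with no control arm. Regression to the mean therefore biases MoCA change.

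The downward direction in the normal cohort follows from the one-sided cut. Its size, about 0.1 to 1.3 points, depends on the assumed error SD, source mean and source SD. The direction in the MCI cohort cannot be determined from the documents. A pooled test tends towards a spurious decline or about zero, so it would not generally favour BCG. An apparent benefit in MCI is a possible misreading, not a consequence of the plan.

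Severity is minor, given the exploratory status of all outcomes. The mismatch between Baseline in 3.2 and Screening in the schedule needs no assumptions, and it covers the FAQ as well as the MoCA. The FAQ shares the timing but is not a named entry cut-off.

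**What to change.** - **3.3.2, 6.4.1 and 8.1:** report MoCA change by cohort descriptively, without a P value, and state that the pre-value was the selection score. Rest the tested cognitive change on RBANS from Baseline to Outcome, which is already collected and is not used for selection.
- **3.2:** describe MoCA and FAQ change as change from Screening.
- **Alternative, if a tested MoCA change is wanted:** add a separate MoCA at the Baseline visit as the reference and keep the Screening score for eligibility only. This removes the selection bias if errors are independent; a practice effect would remain.

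The main fix is wording only and adds no assessment. Its downside is that MoCA change carries no P value. The alternative costs about 15 minutes per participant, the duration given in 6.4.1.

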6.4.2 Repeatable Battery for the Assessment of Neuropsychological Status Update (RBANS)

The RBANS⁵⁵ is a commonly used 25-minute, standardized neurocognitive battery. The RBANS measures five neurocognitive domains, with twelve subtests measuring cognitive decline or improvement with immediate memory (List Learning and Story Memory), visuospatial/constructional (Figure Copy and Line Orientation), language (Picture naming and Semantic Fluency), attention (Digit Span and Coding), and delayed memory (List Recall, List Recognition, Story Memory, and Figure Recall). The RBANS has been shown to be effective at both detecting and characterizing forms of dementia. The Delayed Memory domain has been shown to be particularly sensitive to discriminating mild cognitive impairment (MCI) due to Alzheimer's disease from controls, and also is predictive of cerebral amyloid burden. The RBANS will be administered at the Baseline and Outcome visits.

6.5 Neuropsychiatric Assessments

6.5.1 Neuropsychiatric Inventory Questionnaire (NPI-Q)

The NPI-Q⁵⁷ will rate symptoms in 12 sub-domains of behavioral functioning including: hallucinations, delusions, agitation, dysphoria, anxiety, euphoria, apathy, disinhibition, irritability, aberrant motor activity, eating abnormalities, and night-time behavioral alterations. The NPI-Q will be done at the Baseline and Outcome visits.

6.5.2 Functional Activities Questionnaire (FAQ)

The FAQ^{12,53} is a brief rating scale used to determine a subjects' level of functional independence when performing a range of instrumental activities of daily living (IADLs), with repeat assessments useful for monitoring performance in these areas over time. The FAQ total score (ranging from 0-30) reflects the sum of ordinal ratings

(0 = fully independent, 1 = has difficulty but does by self, 2 = requires assistance, and 3 = dependent) across ten items assessing a variety of functional activities (i.e., preparing a balanced meal, financial management skills, and shopping), with higher scores indicating increasing levels of dependence. For activities not normally undertaken by a person, a score of 1 is assigned if the subject would be unable to complete the task if required, or a score of 0 is assigned if the subject believes they could successfully carry out the task if needed. Overall, the FAQ is a sensitive marker of functional impairment among individuals with varying dementia severity and has been shown to differentiate mild cognitive impairment from early dementia due to Alzheimer's Disease with 80% sensitivity and 87% specificity. The FAQ demonstrates high reliability (exceeding 0.90), takes about 5 minutes to complete, and requires limited rater training to administer. The FAQ will be done at the Screening and Outcome visits.

7 TREATMENT ADMINISTERED

Summary of Investigational Products

	Investigational Products	
Product Name:	Tokyo BCG (JBL, Tokyo, Japan)	Diluent (0.9% sodium chloride for injection)
Dosage Form:	For intradermal injection	For intradermal injection
Unit Dose	1.8-3.9 x 10 ⁶ colony forming units (CFU)/injection of 0.1ml	0.1 mL
Route of Administration	Intradermal injection	Intradermal injection
Physical Description	sterile, freeze-dried; packaged with a sterile, normal saline diluent	BCG diluent
Manufacturer	Japan BCG Laboratory (JBL)	Japan BCG Laboratory (JBL)

7.1 Study Drug

Japan BCG is an approved drug in Japan, and has been sanctioned by UNICEF and WHO as a standard vaccine for the prevention of tuberculosis. BCG has been administered for this purpose for over 100 years on a global basis, with typical distributions of over 50,000,000 doses to newborns per year. The vaccine has also been approved and utilized for treatment of bladder cancer for the past 30 years.

[name] manufactures the only GMP-quality BCG in the world through contract agreements with the Japanese government. This protocol will be reviewed by the Japanese government ethics committee prior to commencement of study activities. Drug-related contracting will occur through [name] who maintains the Master Drug File, coordinates various IND filing around this vaccine and will interface with regulatory affairs management.

The study drugs (BCG vaccine and diluent) are manufactured by Japan BCG (Tokyo, Japan) and will be managed and stored by the study pharmacist in the [name] lab according to the directions provided by the manufacturer in the approved product labeling. The same study pharmacist and study drug have been used for the past 6 years in [name] protocol #2013P002633.

Japan BCG is a freeze-dried preparation made from the Tokyo 172 strain of *Mycobacterium bovis* Bacillus Calmette and Guérin (BCG). Japan BCG is an attenuated BCG product derived from the original attenuated BCG generated by Albert Calmette and Camille Guerin at the Pasteur Institute.

7.2 Study Drug Packaging and Labeling

The Japan BCG drug product is a sterile, freeze-dried preparation of BCG. The drug product is packaged with a sterile, normal saline diluent.

7.3 Study Drug Storage

This drug is stored with 4°C refrigeration.

7.4 Study Drug Preparation

The BCG vaccine is supplied as a 10-dose ampoule. For reconstitution, 1.0 ml of sterile saline is added to the 10-dose ampoule. Each 0.1ml dose is drawn by syringe from the ampoule following reconstitution and administered intradermally. Once reconstituted, the pharmacy provides the study clinic with the pre-filled syringe in a covered surgical tray to prevent light exposure. If the prepared syringe cannot be immediately administered, it will be temporarily stored at 4°C until administration (< 1 hour from reconstitution).

Each ampoule may be used for a maximum of two study participants in this pilot study of 12 participants. In this case, the ampoule will be reconstituted, and the syringes drawn at the same time. As above, the prepared syringes will be covered and stored at 4°C until administration within 1 hour of reconstitution. The remaining unused volume in the ampoule will not be used for additional patients in this pilot trial.

7.5 Dosage and Administration

All subjects will be consented by a study clinician before any of the following procedures are done. The skin site (deltoid region, alternating between first and second dose) is first cleansed with an alcohol or acetone sponge and allowed to dry thoroughly. Next, $1.8\text{--}3.9 \times 10^6$ colony forming units (CFU), reconstituted by the study pharmacist in 0.9% saline diluent within 1 hour, will be administered intradermally via a 15mm, 26-gauge needle.

Dose selection is based on published data illustrating that two doses of BCG in autoimmune type 1 diabetes confer the immune regulatory/inflammation modulation properties that are of interest in the present study.

Specifically, administration of two doses in type 1 diabetes is associated with short term changes in biomarkers with 22 weeks of observations.³⁶ Moreover, two doses of BCG resulted in a clinical correction of HbA1c in type 1 diabetes with stable correction of disease process for 8 years.³⁷

